Weight loss: Question from the Göteborg Quality of Life Instrument, answering "Yes" to the question "Have you suffered any weight loss over the last three months?"

Reduced physical activity: Taking 1–2 or less outdoor walks per week.

Impaired balance: The Berg Balance Scale, reduced balance defined as having a value of 47 or less. Reduced gait speed: Walking four metres with a gait speed of 0.6 metres/second or slower. Visual impairment: The KM chart (Konstantin Moutakis chart), impaired vision defined as having a visual acuity of 0.5 or less.

Impaired cognition: The MMSE, impaired cognition defined as having a score below 25.

Statistical analysis

A power calculation was done based on the primary outcome variable, dependence in activities of daily living (range 0–9) with an assumed difference between the intervention and control groups of one dependence (i.e., dependent in one or more activities of daily living, a clinically relevant difference of importance to the individual as well as the caregiver) and a standard deviation of 2 in both groups. To detect a difference between the intervention and control groups with a two-sided test and with a significance level of α = 0.05 and 80% power, at least 64 participants were needed in each group. To take a potential loss to follow-up into account, a total of 150 persons (75 in the control group and 75 in the intervention group) were initially planned to be included. This was later revised to allow for a higher loss to follow-up (22%) with 78 + 78, equalling a total of 156 participants.

Both descriptive and analytical statistics were used in order to compare groups and to analyse changes over time. Non-parametric statistics were used when ordinal data were analysed. Otherwise, parametric statistics were used. Besides descriptive statistics, the chi^2 and Fisher's two-tailed exact tests to test differences in the proportions among the groups were used. A value of $p \le 0.05$ (two-tailed) were considered significant. The analysis were made on the basis of the intention-to-treat principle, meaning that participants were analysed on the basis of the group to which they were initially randomised. The approach of data imputation was the replacement of missing values with a value based on the median change of deterioration between baseline and follow-up of all who participated in the follow-up.

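### The revised target of 78 per group keeps the required 64 only up to 17.9% loss to follow-up, not the stated 22%

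*Combined protocol and SAP*

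**What the plan says.** All the sample-size figures are in the power calculation that opens the Statistical analysis section. The primary outcome is the number of dependent activities (range 0–9). The calculation uses "an assumed difference between the intervention and control groups of one dependence" and "a standard deviation of 2 in both groups", "with a two-sided test and with a significance level of α = 0.05 and 80% power", and concludes that "at least 64 participants were needed in each group".

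Two allowances for loss follow. At first, "a total of 150 persons (75 in the control group and 75 in the intervention group) were initially planned to be included", with no loss percentage given. The target was then "revised to allow for a higher loss to follow-up (22%) with 78 + 78, equalling a total of 156 participants". No formula is given for either step.

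The end of the same section describes analysis by randomised group, with "replacement of missing values with a value based on the median change of deterioration between baseline and follow-up", taken from everyone who took part in the follow-up. The Material and methods section reports that 155 people were included between March 2016 and December 2018.

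**The concern.** Loss to follow-up is ordinarily a share of the people enrolled. Read that way, an allowance for 22% loss means that 78% of each group should still meet the stated minimum, and 78% of 78 is below 64. The revision was made because higher loss was foreseen, so the figure fails in the very situation it was meant to cover.

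This sentence is the document's only justification for the final sample size. A reader would take from it that 80% power for the primary outcome survives 22% loss. On the plan's own numbers it does not.

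**Working it through.** **Inputs**, all from the power calculation: difference 1, SD 2 in both groups (standardised difference d = 1/2 = 0.5), two-sided α = 0.05, power 80%, minimum 64 per group, targets 75 and then 78 per group, stated loss 22%.

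**Step 1: reproduce the 64.** The normal approximation is n = 2(1.960 + 0.842)² × (SD/difference)² = 2 × 7.849 × 4 = 62.8, so 63 per group. The two-sample t-test gives n = 63.77, so 64 per group. The plan's base figure reproduces exactly with the t-test, and the discrepancy lies only in the allowance for loss.

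**Step 2: apply the stated loss to the stated target.** Expected losses are 0.22 × 78 = 17.2 per group. Observed participants are 78 × (1 − 0.22) = 60.84, about 61. The shortfall against 64 is about 3 per group.

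**Step 3: find the loss each target can bear.** Tolerable loss = 1 − 64/target.

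| Target per group | Losses that leave 64 | Tolerable loss |
|---|---|---|
| 75 (initial) | 11 | 14.7% |
| 78 (revised) | 14 | 17.9% |

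The revision raised the tolerable loss by about 3 percentage points, but not to 22%.

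**Step 4: find the target that 22% would require.** 64/(1 − 0.22) = 82.05, so 83 per group when rounded up (82 × 0.78 = 63.96; 83 × 0.78 = 64.74). Starting from the less strict 63 of the normal approximation gives 63/0.78 = 80.8, so 81. Neither route leads to 78.

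**Step 5: look for the origin of 78.** 64 × 1.22 = 78.08, and 78/64 = 1.219. The figure fits a 22% mark-up on the required number, as opposed to division by the share retained. This is an inference, because the plan shows no derivation.

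**Step 6: size the consequence.** These figures are for a two-sample t-test on observed cases, with difference 1 and SD 2.

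| Observed per group | Power | Difference detectable with 80% power |
|---|---|---|
| 64 | 80.1% | 1.00 (0.998) |
| 60.84 | 78.1% | 1.02 (1.024) |

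At a whole 61 per group the power is 78.2%.

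**The case against.** The best defence is that the text never says what the 22% is a percentage of. The 14 extra participants are 14/64 = 21.9% of the required number, so 78 may be exactly what was intended, with the percentage mislabelled. That probably explains the origin, but it does not rescue the sentence: the 22% is called a loss to follow-up, and a 22% mark-up on 64 protects against only 17.9% loss among those enrolled.

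A second defence is that imputation keeps every randomised participant in the analysis. It does restore the count of analysed records. If the median change is added to a participant's own baseline, which the text does not specify, the filled-in value also carries that baseline. It still supplies no observed follow-up outcome. And if imputed cases counted towards the 64, neither allowance for loss would have been needed.

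Three points on weight do stand:

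- The effect is slight. An SD of about 1.95 (2/1.024) in place of 2 would restore 80% power at about 61 per group, and the plan gives no source for the SD of 2.
- The power figures are t-test figures, while the plan says non-parametric methods were used for ordinal data. They are fair as planning figures because the t-test reproduces the 64, but they need not be the power of the analysis performed.
- The 83 rests on strict rounding up. In whole participants, 82 with 18 lost (21.95%) leaves exactly 64. Either figure is above 78.

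**Conclusion.** The concern holds, and it is minor. On the plan's own inputs, 78 per group preserves the stated minimum up to 17.9% loss; at 22% about 61 per group would be observed, with power about 2 percentage points lower than at 64.

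This rests on two readings: that the 22% is a share of those enrolled, as the term normally means, and that the 64 refers to participants with an observed outcome. The power figures also assume the planned difference and SD and a t-test.

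It is not shown that the trial was underpowered. The document does not report the actual loss, and a shortfall against 64 arises only if loss exceeded 17.9%. Nothing in the conduct of the trial is affected.

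**What to change.** Replace the sentence on the revised target with wording such as:

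> The target was later raised to 78 per group (156 in total). This keeps 64 observed participants per group with up to about 17.9% loss to follow-up (14 of 78). At 22% loss about 61 per group would be observed, giving about 78% power (two-sample t-test, difference 1, SD 2, observed cases).

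The cost is one sentence and a slightly less favourable stated allowance. No further enrolment is asked for, and the data and analysis stay as they are.

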Comprehensive Geriatric Assessment for Frail Older People in Swedish Acute Care Settings (CGA-Swed): A Randomised Controlled Study

NCT02773914

2024-09-10

Study Protocol with SAP and/or ICF

Aim

The aim of the study was to evaluate the effects of the CGA for frail older people in Swedish acute hospital settings. The study addressed the following research questions:

Can the Comprehensive Geriatric Assessment for frail older people in Swedish acute hospital settings:

- 1. Maintain independence in activities of daily living, functional status, health-related quality of life and life satisfaction?
- 2. Increase satisfaction with health care?
- 3. Reduce hospital and primary health care consumption?

How feasible and acceptable are the study processes and procedures of the CGA from the perspective of care givers and older persons in Swedish settings?

Material and methods

The study was a two-armed randomised controlled trial that started with a pilot study in 2016. Ethical approval was obtained for the study, ref. no: 4,899-15, Regional Ethical Review Board in Gothenburg. Trial Registration: ClinicalTrials.gov, NCT02773914.

Data collection and participants: The study group included 155 older people who sought acute medical care at the emergency department during the period between March 2016 and December 2018. Inclusion criteria were that participants were to be ≥75 years of age, in need of acute inhospital care and screened as frail according to the FRESH-screening instrument. Exclusion criteria were not being screened as frail according to the FRESH-screening instrument, being admitted through a "fast track" for direct admission to a designated ward (for predefined diagnosis such as stroke, acute myocardial infarction and hip fracture) and having an acute severe condition requiring a higher level of care (e.g., intensive care) than the intervention ward. Baseline measures were collected by a research assistant who gathered data from the frail older patient and/or from the medical records during the hospital stay. Follow-up interviews were performed in the older person's home at 1, 6 and 12 months after hospital discharge. The follow-ups were performed using a structured questionnaire including questions about demographic data and assessments of outcome measures. The interviews lasted for approximately 1.5 h.

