Intervention/control group: The intervention was the ward working according to the Comprehensive Geriatric Assessment. Key components of the CGA are multi-disciplinary teamwork, use of a personcentred approach, comprehensive assessments, treatment and rehabilitation, discharge planning and follow-up. The multi-disciplinary team consisted of a physician, registered nurse (RN), assistant nurse (AN), physiotherapist (PT) and occupational therapist (OT) as well as other team members, such as a social worker (SW) and dietician, if needed. The control group received the usual acute hospital care, i.e., care given at an ordinary medical hospital ward without a specialised multi-disciplinary team approach and without the CGA. The assessments and care provided at the control wards were based on the acute problem/symptom that the patients had and did not include the comprehensive and person-centred approach to the health and life situation of the patient inherent in a CGA.

Measurements: Dependence in daily activities was measured using the ADL-staircase assessment by combining both interviews and observations. It includes dependence in nine activities: cleaning, shopping, transportation, cooking, bathing, dressing, going to the toilet, transferring and feeding. Dependence was defined as a state in which another person is involved in the activity by giving personal or directive assistance. The sum of dependence in the nine activities of daily living is calculated, range 0−9, with a clinically significant change of ≥1 unit between baseline and follow-up.

Functional status was measured using the Timed Up and Go (TUG) test, the Berg Balance Scale, Gait Speed four-metre walking test and Grip Strength with North Coast Dynamometer. The TUG test measures the time for a person to rise from a chair, walk 3 m, turn around, walk back,

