Life satisfaction was measured using the Fugl-Meyer-Lisat-11 Questionnaire which includes 11 items concerning satisfaction with: life as a whole, work, financial situation, leisure, friends and acquaintances, sexual life, functional capacity, family life, partner relationship, physical health and psychological health. Response alternatives included: very dissatisfied, dissatisfied, rather dissatisfied, rather satisfied, satisfied and very satisfied. In the analysis, the responses to each question were dichotomised into satisfied (very satisfied and satisfied) or not satisfied (rather satisfied, rather dissatisfied, dissatisfied and very dissatisfied) as was done in the validation of the questionnaire. The sum of items for which the respondent reported being satisfied were calculated, range 0–11, with a clinically significant change of ≥1 between baseline and follow-up. Satisfaction with quality of care was measured by the participant's agreement with six statements with a person-centred approach: "I feel that the care given during the hospital stay meets my needs", "I feel that the care planning meeting before discharge was valuable", "I was able to take part in the discussion of my needs in the care planning meeting", "I feel that the actions planned equal my needs", "I feel that the actions delivered equal my needs" and "I am satisfied with the hospital care". The response alternatives were agree completely, agree partly, neither agree nor disagree, disagree, and disagree completely. An answer of agree completely or agree partly were considered as satisfied. These questions were only measured once (at 1 month follow-up) and were used as the difference between intervention and control groups in the proportion of participants being satisfied for each question at follow-up as has been done previously. In this study, we used the following measurements and cut-off levels of frailty indicators: Weakness: Reduced grip strength considered to be below lowest norm range for ages 80-84, 13 kg for women and 21 kg for men for the right hand and below 10 kg for women and 18 kg for men for the left hand, using a North Coast dynamometer. Fatigue: Question from the Göteborg Quality of Life Instrument, answering "Yes" to the question "Have you suffered any general fatigue/tiredness over the last three months?"

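### The 80% power matches an unadjusted comparison of mean ADL scores, but no test, endpoint form, visit or baseline covariate is named for the primary ADL outcome

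*Combined protocol and SAP*

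**What the plan says.** All of this is in the single combined document.

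- **Statistical analysis, power calculation.** The primary outcome is dependence in daily activities (0–9). The assumptions are "an assumed difference between the intervention and control groups of one dependence", SD 2 in both groups, two-sided 0.05 and 80% power, giving 64 per group. On loss to follow-up: "This was later revised to allow for a higher loss to follow-up (22%) with 78 + 78". The formula is not named, nor is it said whether the SD belongs to the score or to its change.
- **Statistical analysis, choice of test.** A general rule: "Non-parametric statistics were used when ordinal data were analysed. Otherwise, parametric statistics were used". The ADL sum is assigned to neither class. The only tests named are chi-square and Fisher's, for proportions: "two-tailed exact tests to test differences in the proportions among the groups were used".
- **Statistical analysis, missing data.** Missing values are replaced using the "median change of deterioration between baseline and follow-up of all who participated in the follow-up".
- **Measurements.** The ADL sum is given "with a clinically significant change of ≥1 unit between baseline and follow-up". A group comparison of proportions is stated for one outcome only, satisfaction with quality of care: "difference between intervention and control groups in the proportion of participants being satisfied for each question at follow-up".
- **Data collection and participants.** Baseline is measured during the hospital stay, and follow-up takes place at "home at 1, 6 and 12 months after hospital discharge". No visit is named as primary.

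No regression model or covariate appears anywhere.

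**The concern.** The 80% belongs to one specific analysis, and the plan does not commit to it. The general rule would admit a t-test, a Mann-Whitney test or a change-score test, at any of three visits. The change threshold leaves a comparison of proportions open as well. These options differ widely in power, and a reader cannot tell whether a reported ADL result is the planned one.

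Baseline ADL must be available, because both the change threshold and the imputation need it. A score comparison that does not adjust for it gives up precision that costs nothing to recover. A change-score analysis would use baseline, but less efficiently than adjustment does.

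**Working it through.** **Inputs from the documents:** difference 1, SD 2, two-sided 0.05, 64 per group, 22% loss, 155 participants, pooled median-change imputation. **Assumed:** correlation r between baseline and follow-up ADL of 0.3/0.5/0.7 (the documents give none); SD 2 as the SD of the score (step 4 takes the alternative); a 78/77 split; loss completely at random; control mean change of 0 to 1 unit.

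**1. The plan's own figure.** Standardised difference 1/2 = 0.5. The two-sample t-test needs 63.77, so 64 per group, with power 80.1%. The figure reproduces. That it is an unadjusted comparison of means is inferred from this match.

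**2. 64 complete cases per arm, normal score.**

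- ANCOVA: residual SD = 2·√(1−r²) = 1.908/1.732/1.428.
- Change score: SD = 2·√(2(1−r)) = 2.366/2.000/1.549.

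| Analysis | r=0.3 | r=0.5 | r=0.7 |
|---|---|---|---|
| Unadjusted t | 80% | 80% | 80% |
| Change-score t | 66% | 80% | 95% |
| ANCOVA | 84% | 90% | 98% |

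**3. With 22% loss.** Simulation of a score rounded and clipped to 0–9, baseline mean 5, 78/77 randomised, true difference 1. Ranges mainly reflect the control mean change. After loss, 78 × 0.78 ≈ 61 remain per arm.

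| Analysis | r=0.3 | r=0.5 | r=0.7 |
|---|---|---|---|
| *Complete cases* | | | |
| Unadjusted t | 75–78% | 75–78% | 75–78% |
| Change-score t | about 60–63% | about 75% | about 92% |
| ANCOVA | 79–82% | 86–88% | 95–96% |
| *Plan's imputation* | | | |
| Unadjusted t | about 65% | about 65% | about 65% |
| Change-score t | 60–63% | 73–75% | 91–92% |
| ANCOVA | about 75% | about 83% | 94–95% |

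With complete cases the mean 95% interval width is 1.41 unadjusted, against 1.35/1.23/1.04 adjusted. ANCOVA's type I error was 4.5–5.8% across both settings. With a baseline mean of 6.5, nearer the ceiling, imputed power was 73–75/81–83/92–94% for ANCOVA and 62–66% for the unadjusted t-test.

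The imputed rows are low for a specific reason. Lost participants in both arms receive baseline plus the same constant, so they contribute no expected treatment difference. The complete-case estimate of 0.95–0.99 (below 1 because of clipping) becomes 0.78 × 0.95 = 0.74 to 0.78 × 0.99 = 0.77, which is what the simulation gives. The ANCOVA estimate shrinks in the same way.

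**4. If SD 2 is the SD of the change.** The change-score t-test then has 80% at 64 per arm. The ANCOVA residual SD is 2·√((1+r)/2) = 1.612/1.732/1.844, giving about 94/90/86%. ANCOVA still leads, but its gain now falls as r rises.

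**5. Conditional case: ADL tested as the proportion worsening by at least one unit.** Chi-square power under the plan's imputation is 36–39/47–50/68–72%. At r=0.7 this slightly exceeds the unadjusted t-test (about 65%), because change already uses baseline.

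**The case against.** **The proportion tests.** Since chi-square and Fisher's are the only tests named, a reader might infer that the primary ADL outcome was tested as a proportion and that the 80% is therefore wrong. The documents do not support this. They state a group comparison of proportions only for satisfaction with care, and the general rule leaves score-based tests open. Step 5 is a scenario.

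**The fall from 80% to 65%.** A reader might attribute this to the missing covariate. It is mainly the effect of loss plus imputation. With complete cases after the same loss the unadjusted test keeps 75–78%, and at r=0.3 ANCOVA adds only a few points. The shrunken estimate is a separate problem that adjustment leaves in place.

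**Baseline may already be used.** The plan speaks of analysing changes over time and defines an ADL change threshold, so a change-score analysis is a plausible reading. If that is what was done, baseline is not ignored. This stands in part: the reading is not stated, and change scores had lower power than ANCOVA in every scenario run.

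**Validity and timing.** An unadjusted test is valid under randomisation, so adjustment is a matter of efficiency whose size depends on an assumed r. Recruitment ended in December 2018 and the document is dated 2024, so a new model may carry only post hoc weight. Both points stand and limit how strongly the change can be urged.

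**Conclusion.** The concern holds as a specification gap together with a missed gain in precision. It does not show an invalid analysis or a wrong sample size. The gap follows from the text: no ADL test, endpoint form, primary visit or covariate is named, so the 80% cannot be tied to one analysis.

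The size of the gain rests on the assumed r, random loss, a true difference of one activity and SD 2 as the SD of the score. Adjustment adds roughly 4 to 18 points of power over the unadjusted t-test with 64 complete cases per arm (84 − 80 to 98 − 80), and roughly 10 to 30 under the plan's imputation (75 − 65 to 95 − 65). ANCOVA had the highest power in every scenario examined, but it does not always reach 80%: at r=0.3 under imputation it has about 75%. The change is worth making. Confidence is high on the gap and moderate on the size of the gain.

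**What to change.** Name one primary ADL analysis: the full 0–9 score at one named follow-up, compared between arms with arm and baseline ADL as terms, reported with a 95% interval. Use ANCOVA, or proportional odds if the score is treated as ordinal. In simulation under the plan's imputation (control change 0.5), proportional odds had 70.8/80.9/94.1% power, against 75.5/84.5/95.6% for ANCOVA in the same runs. Keep the proportion with a change of at least one unit as a supporting summary.

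State whether SD 2 refers to the score or the change. If a proportion test was in fact primary, replace the 80% with that test's power and give the event rates assumed. If the adjusted analysis is adopted after results are known, label it post hoc and show it beside the unadjusted result. The imputation needs its own correction.

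The cost is SAP wording and one regression on data already collected, with no new participants or visits. The drawbacks are limited weight if post hoc and, with proportional odds, an odds ratio that is harder to read than a difference in number of activities.

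### As written, the fill for missing values makes no use of a participant's own earlier follow-up visits, so a recorded decline can be undone and the ≥1-unit ADL change misclassified

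*Combined protocol and SAP*

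**What the plan says.** The combined protocol and SAP gives one imputation rule, at the end of the Statistical analysis section: "replacement of missing values with a value based on the median change of deterioration between baseline and follow-up of all who participated in the follow-up". The same section describes the analysis as intention-to-treat, meaning that "participants were analysed on the basis of the group to which they were initially randomised".

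Under Data collection and participants: "Follow-up interviews were performed in the older person's home at 1, 6 and 12 months after hospital discharge". A participant can therefore have one or two follow-up values before a missing one.

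Under Measurements, the ADL-staircase score is defined: "The sum of dependence in the nine activities of daily living is calculated, range 0−9". The threshold that the plan attaches to this score reads: "with a clinically significant change of ≥1 unit between baseline and follow-up".

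The plan mentions no longitudinal model, multiple imputation or sensitivity analysis for missing data. It names no primary time point among the three visits.

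**The concern.** The rule names three ingredients: baseline, the follow-up in question, and the median change of those who attended it. A participant's own intermediate values are not among them. Someone interviewed at 6 months and then lost would get a 12-month score that ignores what was recorded at 6 months. Someone who missed only the 6-month visit would be filled in the same way, despite having values on both sides.

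Two things are at stake. A filled score may contradict the participant's own record, showing a recovery that nobody observed. And because every filled participant receives the same change, the fill cannot separate those who deteriorated by at least one unit from those who did not. This is distinct from taking the median over both arms together: it would remain if the median were taken within each arm.

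**Working it through.** **1. The plan's own figure.** The plan gives no figure for the imputation. Its sample-size inputs, used below as simulation settings, are "an assumed difference between the intervention and control groups of one dependence", "a standard deviation of 2 in both groups", "with a two-sided test and with a significance level of α = 0.05 and 80% power". The normal approximation gives 2 × (1.960 + 0.842)² × 2² / 1² = 62.8, so 63. The t-test version gives 63.77, so 64, as stated. This point does not affect that figure.

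**2. The rule as arithmetic.** Let b be baseline ADL, y6 the observed 6-month score and m the median baseline-to-12-month change. On the natural reading, the filled 12-month score is min(9, b + m). It is better than the last observed score whenever y6 − b > m. The documents do not give m, so 0 to +2 is an assumed range. For b = 2 and y6 = 5:

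| m | Filled 12-month score | Observed loss reversed |
|---|---|---|
| 0 | 2 | 3 |
| +1 | 3 | 2 |
| +2 | 4 | 1 |

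**3. Effect on the ≥1-unit criterion.** The filled change equals m for everyone, apart from the cap at 9. With m = 0, every filled participant is classed as not deteriorated, including those with a recorded decline. With m = +1, every filled participant is classed as deteriorated (unless capped), including those stable at their last visit.

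**4. Precision of a filled value.** Take an SD of change of 2 (the plan's SD, applied here to change), random dropout, and correlation ρ between 6- and 12-month change:
- Baseline plus median: error about 2.
- Own 6-month value plus the typical later change: 2√(2(1 − ρ)), which is 1.79, 1.55 and 1.26 for ρ = 0.6, 0.7 and 0.8. At ρ = 0.5 it is 2.0, so there is no gain.
- Prediction from a model using the 6-month value: 2√(1 − ρ²), which is 1.60, 1.43 and 1.20, and 1.73 at ρ = 0.5.

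**5. Simulation.** From the plan: 78 per arm, a true difference of 1.0, SD 2 and 22% missing. Assumed: mean 12-month change +1 in control and 0 under CGA, ρ from 0.6 to 0.8, all losses after the 6-month visit, and dropout either random or rising with 6-month decline (log-odds up to 0.5 per unit). Medians are taken within arm, to separate this point from the pooling.

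| | Arm-median fill | Own 6-month value |
|---|---|---|
| Mean difference, random dropout | about 1.0 | about 1.0 |
| Mean difference, ρ = 0.7, log-odds 0.5 (full data 1.00) | about 0.92 | about 1.02 |
| Root-mean-square fill error, all settings | about 2.0–2.4 | about 1.3–2.0 |
| Filled participants misclassified on ≥1 unit, all settings | about 41–50% | about 17–30% |

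The sampling SD of the estimated difference is about 0.33, so the isolated shift of up to about 0.1 is small beside it.

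**6. In participants.** 22% of 156 is 34.3. Misclassification of 41–50% is about 14 to 17 people (34.3 × 0.41 = 14.1; × 0.50 = 17.2). At 17–30% it is about 6 to 10 (34.3 × 0.17 = 5.8; × 0.30 = 10.3). These counts assume that all have a 6-month value.

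**The case against.** - **The rule is inferred.** The text says the value is based on the median change. It does not say that it is added to baseline, nor that interim values are excluded. A reader might infer that the plan forbids their use; it is only silent. This stands, and is itself a reason to state the rule exactly.
- **Much of the apparent bias belongs to the pooling.** In the simulation at ρ = 0.7 and log-odds 0.5, the median pooled over arms gives a difference of about 0.70. A reader might attribute that fall to the neglect of interim visits. Pooling alone already brings it to about 0.79 under random dropout, where neglecting interim visits adds no bias. Only the arm-median result, about 0.9, belongs here.
- **A reversed decline is not always a misclassified one.** Take baseline 3, 6-month score 8 and a median of +1. The filled score is 4: four activities appear recovered, yet a change of +1 still meets the criterion. A worsened participant is lost from the count only if the median is below 1.
- **The number affected is unknown.** A reader might suppose that most of those lost have an interim value, but the documents give no timing of losses. If half of those missing had no 6-month value, the gain in fill error over arm medians would shrink from about 0.6 to 0.28 units (ρ = 0.7, log-odds 0.5). A value missing at 1 month has no earlier follow-up visit behind it.
- **The simple alternative is imperfect.** Filling from the last value overshoots slightly when dropout follows decline (up to about 1.06 for a true 1.0) and gains nothing at ρ of about 0.5. This favours a model over another single fill.

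**Conclusion.** The point holds as a worthwhile improvement, not as evidence of a seriously biased treatment effect. As written, the plan describes no use of a participant's earlier follow-up visits, and the filled score can be better than the last observed one whenever the recorded decline exceeds the median. That much is arithmetic on the natural reading of the rule.

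The size rests on assumptions. Apart from pooling, the mean difference is unaffected under random dropout and moves by up to about 0.1 of a true 1.0 if dropout follows 6-month decline. The main cost is imprecise fills and misclassification on the ≥1-unit criterion, with the simulated rates shown above. The benefit is smaller if some losses precede any follow-up visit or the correlation is lower. Neither the actual median change nor the timing of losses is in the documents, so confidence in the size is moderate.

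**What to change.** Analyse ADL with a longitudinal model (a mixed model for repeated measures or an ordinal equivalent), or by multiple imputation within arm, using baseline and all attended visits. Keep the median fill only as a sensitivity analysis, with its formula written out, including whether the change is added to baseline. Report, by arm and visit, how many values were filled and how many of those participants had an earlier observed follow-up visit.

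No new data are needed. Inclusion ended in December 2018 and the analysis is described in the past tense, so the cost is a re-analysis with a somewhat more complex method, not just a change of wording. Values missing at the 1-month visit gain least, since no earlier follow-up visit exists.
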